**3) IRB Review History**

*N/A*

**4) Objectives**

The purpose of this study is to determine whether the use of the embrace device after repair of linear cutaneous surgery wounds improves scar cosmesis. We will use a split wound model, half of the wound is treated with the embrace device and the other half is not treated. Three-months post-surgery, the scar will be measured via the physician observer scar assessment scale, a validated scar instrument. The scar width and adverse events will also be recorded.

**5) Background**

Following the surgical repair of cutaneous wounds, scar formation is inevitable and results in varying degrees of aesthetic and/or functional impairment. Numerous treatment modalities have been employed to treat scars. Carbon dioxide and pulse dye lasers, as well as dermabrasion can reduce erythema and irregular topology of the scar surface. Silicone-based products have also been used to treat post-surgical scars, including gels, sheets, and tape. Intralesional steroids are often injected into to induce flattening of a scar. More recent research has highlighted the impact of mechanical forces and tension on scar formation. In one report, incisions in both pigs and humans were treated with a tension-shielding device and showed a reduction in scarring. More recently two clinical trials have been published in the plastic surgery literature showing that the use of the embrace device, a silicone-based dressing designed to minimize wound tension, is effective in improving the aesthetic outcome following scar revision surgery. While these initial studies of the embrace device have promising findings, there are significant drawbacks to both studies including small study population, inclusion of patients seeking scar revision (a select group likely predisposed to poor scar cosmesis and not representative of first-time surgical patients), investigator conflict of

PROTOCOL TITLE: Use of embrace device after cutaneous wound closure: a randomized split wound comparative effectiveness trial

interest, and the use of a digital software-based scar assessment tool using patients photos that were not standardized with respect to lighting or distance. Therefore, larger studies in first-time surgical patients with standardized photos for scar assessment are required to validate this potentially promising device for improved scar cosmesis.

## **6) Inclusion and Exclusion Criteria**

All patients scheduled for cutaneous surgical procedures with one of the study investigators at the UC Davis Department of Dermatology will be screened for eligibility.

### **Inclusion Criteria:**

- 18 years of age or older
- Wound defect diameter of at least 1cm on the face and 1.5cm on the body
- Able to give informed consent themselves
- Patient scheduled for cutaneous surgical procedure along a non-concave surface suitable to application of the embrace with predicted primary closure over a high tension area
- Able to apply dressings themselves or have someone else apply it for them
- Willing to return for follow up visits.

### **Exclusion Criteria:**

- Cognitively Impaired
- Incarceration
- Under 18 years of age
- Wounds with predicted closure length less than 3 cm
- Wounds that are less than 1cm in diameter on the face and 1.5cm on the body
- Patients with known adverse reactions to adhesives
- Patients with history of collagen vascular disease

None of these special populations will be included: adults who are unable to consent, individuals who are not yet adults (under the age of 18), or prisoners.

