Patients will be taught how to apply the embrace device at the initial study visit. We will also ask that patients watch a short youtube video found at [youtube.com/EmbraceScarTherapy](https://www.youtube.com/EmbraceScarTherapy) prior to initial self application. Following the subcuticular sutures placement, patients will receive a phone call from study personnel to assess the wound for an infection. 10-14 days after the procedure study personnel will conduct a phone call and conduct a questionnaire to assess the status of your wound. If study subjects indicate they have redness beyond the immediate wound edge, pus, or pain at the wound site and an infection is suspected the study subject will be scheduled for a visit to assess the wound and will be

PROTOCOL TITLE: Use of embrace device after cutaneous wound closure: a randomized split wound comparative effectiveness trial

withdrawn from the study if an infection is present. If the wound is healing properly, then subjects will be told to begin using the Embrace device, and to allow the device to remain in place for 10 days. Patients will replace the device every 10 days for 3 months.

Follow-up assessment will be scheduled for three months following the procedure, with a one-month window before or after that time if the patient cannot return at precisely three months.

At the follow-up visit, two blinded observers will record their scores independently using the physician observer scar assessment score instrument (POSAS). The width of the scar on both sides will also be measured and recorded 1 cm from midline on both sides of the scar. The patient part of the instrument will be independently recorded and a copy of the patient (POSAS patient scale) questionnaire has been uploaded to IRBnet. This data will be recorded in the redcap database. The scoring will be of the participant's wound on the day of the follow-up. Digital images will then be obtained again, which may be used for scientific meeting presentation and/or publication purposes. These images will be stored for a maximum of two years following study completion.

*Describe:*

- *Procedures performed to lessen the probability or magnitude of risks.*

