All adverse events will be monitored and recorded. Safety precautions will be the same as for all patients undergoing cutaneous procedures. Patients will be given instructions to call in the event of any complications such as bleeding, infection, pain or any concerns. An on call resident will be available by phone at all hours, every day of the week. Instructions for contacting the on call resident will be given in written form as well.

- *All drugs and devices used in the research and the purpose of their use, and their regulatory approval status.*

*The embrace device (FDA Cleared) will be used to cover half of each surgical wounds.*

- *The source records that will be used to collect data about subjects. (Attach all surveys, scripts, and data collection forms.)*

We will collect all data, demographic and scientific, in the redcap data collection system. The patient will be queried for demographic data verbally or the patient chart will be examined within the EMR to obtain the date of birth, race, gender, date of surgery, date of follow-up, name,

PROTOCOL TITLE: Use of embrace device after cutaneous wound closure: a randomized split wound comparative effectiveness trial

medical record number, and surgery location. All other data will be recorded from assessments during study evaluation.

- *What data will be collected including long-term follow-up.*

POSAS scores, width of the scar at follow-up, digital images, occurrence of any complications including: spitting sutures, dehiscence, infection, necrosis, bleeding, and hematoma.

- *Describe how much blood is being drawn and how often*

NA

*b) Humanitarian Use Device (HUD)*

*For HUD uses provide a description of the device, a summary of how you propose to use the device, including a description of any screening procedures, the HUD procedure, and any patient follow-up visits, tests or procedures.*

NA

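### The device is described as silicone-based, but the only material-related exclusion is for adhesives, so a patient with a known silicone reaction is eligible as written (minor safety point)

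*Combined protocol and SAP*

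**What the plan says.** The Background (section 5) describes "the embrace device, a silicone-based dressing designed to minimize wound tension". It also lists silicone gels, sheets and tape among products already used on post-surgical scars.

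The exclusion criteria (section 6) contain one item on tolerance of a material: "Patients with known adverse reactions to adhesives". The only other exclusion based on medical history is "Patients with history of collagen vascular disease". The rest concern cognition, incarceration, age, closure length and wound diameter. In the inclusion criteria, the phrase that mentions the device is "along a non-concave surface suitable to application of the embrace".

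Section 12 (Procedures Involved) says that the device "will be used to cover half of each surgical wounds". On timing it says "10-14 days after the procedure study personnel will conduct a phone call", and subjects are told to begin wear if the wound is healing properly. It then says "Patients will replace the device every 10 days for 3 months". The complications named for collection are "spitting sutures, dehiscence, infection, necrosis, bleeding, and hematoma".

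**The concern.** The plan already accepts that a known intolerance of something in the device should keep a patient out, because it excludes known adhesive reactions. It does not apply the same principle to silicone, the one material it uses to describe the device. Silicone products are in common use on scars by the protocol's own account, so it is plausible that a few patients have met the material before and know that they react to it.

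What is at stake is an avoidable exposure. A patient with such a history could be enrolled and asked to wear the dressing for weeks, although one question at screening would have identified the problem. Section 18 states no direct benefit to individual subjects, so there is little to set against a risk that can be screened out.

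**Working it through.** The plan gives no figure on this point, so the check is mainly a reading of the passages side by side.

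**1. Do the criteria catch the patient?** Take a patient with a known silicone reaction, no known adhesive reaction, and otherwise suitable.

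| Place in the protocol | What it tests | Catches this patient? |
|---|---|---|
| Section 6, exclusion on adhesives | Known reaction to adhesives | No, unless adhesive is read to include silicone |
| Section 6, exclusion on collagen vascular disease | A different medical history | No |
| Section 6, other exclusions | Cognition, incarceration, age, wound size, closure length | No |
| Section 6, inclusion phrase on suitability | Shape of the wound surface | No, it does not concern tolerance of the material |
| Section 6, other inclusions | Age, wound size, consent, ability to apply dressings, return visits | No |

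There is no allergy condition and no investigator-discretion clause. The patient is eligible as written.

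**2. Does a later step screen for it?** The call at 10-14 days asks about signs of infection and takes place before wear begins, so it cannot detect a reaction to the device. No question about materials is described there or when application is taught. No further scheduled contact is described until the three-month visit; in between, detection depends on the patient calling. The named complications include no skin or contact reaction, although section 11 says that all adverse events will be recorded.

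**3. How long is the planned wear?** Take 3 months as about 90 days (assumption).
- If wear ends at the three-month visit: 90 − 14 = 76 days (76/7 = 10.9 weeks) to 90 − 10 = 80 days (80/7 = 11.4 weeks).
- If the 3 months run from first application: 90/7 = 12.9 weeks.

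Planned wear is therefore about 11 to 13 weeks on half of the wound.

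**4. What would excluding such patients cost in recruitment?** Section 23 gives about 30 cutaneous surgery patients a week, and section 7 requires 50 in total. Not all of the 30 would be eligible, but the loss of a rare patient would not be noticed.

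**The case against.** The two sections do not contradict each other: a silicone-based dressing can be held on by an adhesive. The documents never say what that adhesive is. If it is silicone, a site might read the present exclusion as already covering some silicone reactions. This stands as a limit on the point, but it also shows that the wording is open to two readings.

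The documents report no silicone reaction. Section 15 says that two earlier trials of the intervention had no adverse events, although a stray question mark in that sentence weakens it. The Background places the research need in patients having surgery for the first time, who are less likely to have used silicone on an older scar, though first-time status is not an eligibility criterion. A patient who knows of a reaction may well mention it during consent or when application is taught. The consent pages were not available for this review, so what they say about materials is unknown. All of this supports a very small number of affected patients. None of it closes the gap in the list.

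A patient who reacts need not go on wearing the device for the whole period. Section 12 tells patients to call with complications or concerns and provides an on-call resident, section 15 has safety data reviewed weekly, and section 16 lets subjects stop at any time. These provisions limit continued exposure; they do not prevent the first exposure.

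A reader might also infer that the gap biases the trial, because a reaction would fall on the device half alone and would not cancel in the paired difference. The documents do not support that. They give neither a frequency of reactions nor an effect of a reaction on the scar score, so any shift would have to be invented. Its direction would be against the device, so it could not create a false claim of benefit. A patient who left the study because of a reaction would contribute no such shift.

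**Conclusion.** The point holds as a minor gap in eligibility and safety wording. Under the criteria as written, a patient with a known silicone reaction and no known adhesive reaction can be enrolled and told to wear the device on half of the wound, and no later step screens for this.

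The size cannot be estimated from the documents: they give no reaction rate. The number affected is probably very small. No material effect on the primary result is shown, and the sample size, power and primary analysis are not in question. The conclusion rests on taking the Background's description of the device at face value and on reading the adhesive exclusion literally, since the make-up of the adhesive is not stated.

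**What to change.** Reconcile the exclusion in section 6 with the device description in section 5. The known-reaction exclusion, and the question asked at screening, should cover the device's stated material (silicone) as well as adhesives. When doing so, the sponsor should check the wording against the device's actual materials, including its adhesive, so that only one reading is possible.

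The cost is a few words in the criteria and one screening question. The downside is that the rare patient with such a known reaction is not enrolled, which is negligible for recruitment.

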## **7) Number of Subjects**

- a) Study- Wide:

PROTOCOL TITLE: Use of embrace device after cutaneous wound closure: a randomized split wound comparative effectiveness trial

This is a single center study; see below.

b) Local: We will enroll 50 patients locally in this single center study.

## 8) Recruitment Methods

a) Study-Wide:

Patients will be recruited from the investigators surgical practices at the time of the procedure at the University of California, Davis, Dept. of Dermatology.

The surgical schedule will be examined to identify potential study subjects. Faculty will be reminded about the study through a flier posted in the doctors charting lounges (Attached).

The patients name, age, gender, medical record number, operative and follow up images and phone number will be recorded in the Redcap data system to allow study personnel to contact patients to arrange their follow up visits. Information will be deleted from the redcap system after 3 years. HIPPA authorization will be obtained from each patient.

## 9) Compensation to the Subjects

No compensation provided to study subjects.

## 10) Study Timelines

The duration of an individual subject's participation in the study is 3-12 months.

The duration anticipated to enroll all study subjects is 12 months and the estimated date for the investigators to complete this study (to complete primary analyses) is 12 months.

## 11) Study Endpoints

*Describe the primary and secondary study endpoints.*

The primary endpoint will be the two blinded reviewers sum of the component parts of the patient observer assessment score(POSAS) at a three-month assessment visit.

The secondary endpoint will include the width of the scar at the follow-up, patient POSAS sum score, POSAS overall opinion scores for both the observers and the patient, and any complications from the treatment.

*Describe any primary or secondary safety endpoints.*

Cutaneous surgery is a very low risk procedure. No deaths have ever been observed in our department, minor infections occur at rates of < 3% and

PROTOCOL TITLE: Use of embrace device after cutaneous wound closure: a randomized split wound comparative effectiveness trial

bleeding and dehiscence at much lower rates still. All adverse events will be recorded, and monitored. Serious adverse events will be reported, though none are expected.

## 12) Procedures Involved

### *a) Describe and explain the study design.*

This is a single center, randomized, evaluator blind, split scar study.

*Provide a description of all research procedures being performed and when they are performed, including procedures being performed to monitor subjects for safety or minimize risks.*

After screening and informed consent, demographic data will be collected including date of birth, race, gender and medical record number. This will be collected in the redcap database.

Each half of the wound will be labelled with an A or a B. A horizontal wound will be labelled A on the left half and B on the right half. A vertical wound will be labelled A on the upper half and B on the lower half. The patient's wound will be labeled A if it is on the left or superior side of the investigator and B if it is on the right or inferior side. The wound will be labeled before the wound suturing so the wound healing can be effectively determined. The wound is labelled using a surgical marker. Subcuticular sutures (either vicryl or pds, depending on surgeon's preference) will be placed equally on both halves of the wound and 5-0 fast absorbing gut epidermal sutures will be placed equally on both halves of the wound. After the sutures are placed, a predetermined, concealed randomization number will be obtained from the RedCap randomization module, which will specify how side A is to be treated. This randomization number is computer generated. Side B will be treated the opposite way as A. Post-operative digital images will then be obtained; these may be used in scientific talks and/or for publication purposes. Treatment assignment, wound length, demographic data, and digital images will be recorded within the redcap database.

Patients will be taught how to apply the embrace device at the initial study visit. We will also ask that patients watch a short youtube video found at [youtube.com/EmbraceScarTherapy](https://www.youtube.com/EmbraceScarTherapy) prior to initial self application. Following the subcuticular sutures placement, patients will receive a phone call from study personnel to assess the wound for an infection. 10-14 days after the procedure study personnel will conduct a phone call and conduct a questionnaire to assess the status of your wound. If study subjects indicate they have redness beyond the immediate wound edge, pus, or pain at the wound site and an infection is suspected the study subject will be scheduled for a visit to assess the wound and will be

PROTOCOL TITLE: Use of embrace device after cutaneous wound closure: a randomized split wound comparative effectiveness trial

withdrawn from the study if an infection is present. If the wound is healing properly, then subjects will be told to begin using the Embrace device, and to allow the device to remain in place for 10 days. Patients will replace the device every 10 days for 3 months.

Follow-up assessment will be scheduled for three months following the procedure, with a one-month window before or after that time if the patient cannot return at precisely three months.

At the follow-up visit, two blinded observers will record their scores independently using the physician observer scar assessment score instrument (POSAS). The width of the scar on both sides will also be measured and recorded 1 cm from midline on both sides of the scar. The patient part of the instrument will be independently recorded and a copy of the patient (POSAS patient scale) questionnaire has been uploaded to IRBnet. This data will be recorded in the redcap database. The scoring will be of the participant's wound on the day of the follow-up. Digital images will then be obtained again, which may be used for scientific meeting presentation and/or publication purposes. These images will be stored for a maximum of two years following study completion.

*Describe:*

- *Procedures performed to lessen the probability or magnitude of risks.*

All adverse events will be monitored and recorded. Safety precautions will be the same as for all patients undergoing cutaneous procedures. Patients will be given instructions to call in the event of any complications such as bleeding, infection, pain or any concerns. An on call resident will be available by phone at all hours, every day of the week. Instructions for contacting the on call resident will be given in written form as well.

- *All drugs and devices used in the research and the purpose of their use, and their regulatory approval status.*

*The embrace device (FDA Cleared) will be used to cover half of each surgical wounds.*

- *The source records that will be used to collect data about subjects. (Attach all surveys, scripts, and data collection forms.)*

We will collect all data, demographic and scientific, in the redcap data collection system. The patient will be queried for demographic data verbally or the patient chart will be examined within the EMR to obtain the date of birth, race, gender, date of surgery, date of follow-up, name,

PROTOCOL TITLE: Use of embrace device after cutaneous wound closure: a randomized split wound comparative effectiveness trial

medical record number, and surgery location. All other data will be recorded from assessments during study evaluation.

- *What data will be collected including long-term follow-up.*

POSAS scores, width of the scar at follow-up, digital images, occurrence of any complications including: spitting sutures, dehiscence, infection, necrosis, bleeding, and hematoma.

- *Describe how much blood is being drawn and how often*

NA

*b) Humanitarian Use Device (HUD)*

*For HUD uses provide a description of the device, a summary of how you propose to use the device, including a description of any screening procedures, the HUD procedure, and any patient follow-up visits, tests or procedures.*

NA

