## **26) Provisions to Protect the Privacy Interests of Subjects**

Only study personnel and nurses normally present during cutaneous procedures and follow-ups will be present. Personal information will be obtained just once at study recruitment. It will not be required at follow up.

Examination of the wound will not differ significantly in practice from standard medical care, during which a faculty member and resident and nurse typically participate in the patients care. In this situation, the number of interactions will be the same or less, since only two study investigators will be required. Medical students will not participate in study patient follow-up evaluation.

PROTOCOL TITLE: Use of embrace device after cutaneous wound closure: a randomized split wound comparative effectiveness trial

*Indicate how the research team is permitted to access any sources of information about the subjects.*

Access to study information will be permitted only for data entry and for study monitoring. Study staff will be requested to only access this information for these purposes only.

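### No step takes the device off the treated half before blinded scoring, so a visit made before the device course ends could reveal allocation to the observers (minor)

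*Combined protocol and SAP*

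**What the plan says.** All the scheduling is in section 12 (Procedures Involved) of the combined protocol and SAP.

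- **Start and wear.** After a wound-check call at day 10-14, patients whose wound is healing well are told to begin, and "to allow the device to remain in place for 10 days". Then: "Patients will replace the device every 10 days for 3 months". The date from which the 3 months are counted is not given.
- **Coverage.** The device "will be used to cover half of each surgical wounds"; the other half is the untreated control.
- **Visit.** The assessment is counted from surgery and set at three months, "with a one-month window before or after that time if the patient cannot return at precisely three months".
- **Scoring.** At that visit "two blinded observers will record their scores independently". They rate the wound itself on the day, not a later photograph. Section 11 makes this observer rating the primary endpoint, and section 12 calls the study evaluator-blind.
- **Who is in the room.** Section 26, on privacy, says: "Only study personnel and nurses normally present during cutaneous procedures and follow-ups will be present".

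No section says when the device comes off before the visit, who removes it, or that the observers must not see it in place.

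**The concern.** The patient knows which half was treated, so the observer rating is the only blinded scar-scale assessment in the trial. It is also a subjective rating of two halves seen side by side. An observer who finds the device on one half, or sees a fresh adhesive outline there, knows the allocation before scoring. In a split-wound design that knowledge bears directly on the within-patient difference that the paired t-test analyses. The schedule makes the situation foreseeable: wear is continuous, the device covers one half only, and the visit can fall before the course is over. What is at stake is how well the blind on the primary outcome is protected. The validity of the within-patient comparison of timing is not in question.

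**Working it through.** **Inputs.** Section 12 gives device start at about day 10 to day 14, a 3-month course, and a visit at 3 months from surgery with one month either side. Section 14 gives a difference of 3 points, SD 7, alpha 0.05, 80% power, 10% dropout, 50 enrolled and at least 45 analysed. I take 1 month as about 30.4 days, so months 2, 3 and 4 fall on about days 61, 91 and 122.

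**Step 1: reproduce the plan's sample size.** For a two-sided paired t-test, with 7 as the SD of the paired differences, the noncentrality is (3/7) × √45 = 2.87 on 44 degrees of freedom. Power is 80.3%, and n=45 is the smallest n that reaches 80%. Allowing for 10% dropout, 45/0.90 = 50. The plan's figures reproduce and are not in dispute.

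**Step 2: when the course ends.**

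- Counted from first application: 10 + 91 = day 101 to 14 + 91 = day 105.
- Counted from surgery: about day 91.

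**Step 3: is the device on at the visit, if the schedule is followed?**

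| Visit | Device days so far | Course from first application | Course from surgery |
|---|---|---|---|
| Early limit, day 61 | 61 − 14 = 47 to 61 − 10 = 51 | on; 40-44 days left | on; 30 days left |
| On schedule, day 91 | 91 − 14 = 77 to 91 − 10 = 81 | on; 10-14 days left | ends at about that day |
| Late limit, day 122 | 91, or 77-81 if from surgery | off | off |

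An early-limit visit finds the device in use on either reading. An on-schedule visit does so on the first reading. On the second, the device comes off at about the time of the visit. This is deduced from the wear schedule; no section states it outright.

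**Step 4: what a short device-off interval would cost.** Removing the device 2 days before an on-schedule visit leaves 75 of 77 or 79 of 81 device days, a loss of about 2.5%. If benefit were proportional to device days (an assumption), the 3-point difference would become 3 × 75/77 = 2.922 to 3 × 79/81 = 2.926. The noncentrality is then (2.922/7) × √45 = 2.80, and power at n=45 is 78.2-78.3%. If benefit has levelled off by then, nothing is lost.

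**The case against.** The protocol does commit to blinded observers. Section 23 says that staff will have printed algorithms and database prompts to guide the procedure and data capture. Those cannot be seen, and a removal step may already be in them. The early visit is an exception for patients who cannot attend on time, and the documents do not say whether the device leaves marks. All of this stands. It is why the frequency is unknown and the grade is low. It does not put a removal step into the protocol text.

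Four stronger readings are tempting, and the documents do not support them.

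- **The observers will be unblinded and the result biased.** The text is silent on removal. Staff may well take the device off first.
- **The variable visit date confounds the comparison.** Both halves are scored on the same day, so timing is identical for treated and control.
- **Early visits cost a known amount of power, so the early side of the window should go.** The documents give neither the share of off-schedule visits nor how benefit depends on wear, so no loss can be calculated. Removing the early side would trade an unshown gain against lost visits. The difference at three months with device use as it occurs is also a legitimate target.
- **Only the observers are there to remove the device**, from the phrase "since only two study investigators will be required" in section 26. That section compares staffing with usual care for privacy purposes. It assigns neither removal nor scoring, and it lists nurses as present.

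**Conclusion.** The point holds as a minor gap in protecting the blind. Followed as written, the schedule puts the device on the treated half on the day of any visit before the course ends. That means early-window visits on either reading, and on-schedule visits as well if the course runs from first application. The protocol text has no device-off interval and names no non-observer to remove the device before the primary rating. Whether this would unblind anyone depends on two things that the documents do not show: whether the device leaves visible marks, and what the staff guides say. The size of any bias therefore cannot be estimated. The sample size, the visit window and the paired comparison are unaffected. The missing start point for the 3-month course is a matter for clarification. It does not change the endpoint, which is fixed at three months after surgery.

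**What to change.** A short amendment to section 12:

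1. Tell patients to remove the device a short fixed interval before the assessment visit, for example 2 days, with the length chosen by the investigator.
2. Have the nurse or other non-observer staff already present confirm that the device is off and the skin is clean before the observers enter.
3. Ask patients not to say which half was treated.
4. As clarifications, state whether the 3 months run from surgery or from first application, and record device start and stop dates. These dates are not among the data items listed in section 12; if the forms already capture them, nothing more is needed.

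Keep the three-month endpoint, the visit window and the 50 patients. No visit or staff member is added. The cost is the 2 device days worked out above, at most about 2 percentage points of power under proportional benefit for on-schedule visits. The 2-day figure is only an example: nothing in the documents shows how quickly marks fade, so the investigator should set the interval from experience with the device. If the staff guides already contain a removal step, moving it into the protocol is enough.
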